b Additional samples for CBC may be collected outside of the protocol-specified time points to ensure a WBC level $\leq 20 \times 10^3/\mu\text{L}$ for the repriming cycle.

c Peripheral smears will be collected and assessed locally.

d Samples for PK and biomarker studies will be collected predose within 12 hours prior to study treatment administration.

- e Vital signs prior to infusion/injection of study treatment. Weight at Day 1. Details are provided in Section 5.1.5.
- f Premedication is required prior to the administration of the first 4 doses of study treatment and in case of reintroduction with repriming. Premedication for subsequent cycles may be continued based on the treating physician's clinical judgment and the presence/severity of prior infusion-related reactions. In the case of a Grade 3 infusion-related reaction, a premedication regimen for subsequent cycles is required (Section 6.5).
- g Magrolimab or saline placebo should not be given on consecutive days. During repriming, the duration of each magrolimab/placebo infusion including flush will be 3 hours (\pm 30 minutes) for the first 3 doses of treatment and 2 hours (\pm 30 minutes) for infusions beyond the first 3 doses. All participants should be monitored for 1 hour after infusion for doses during the first 28 days and the repriming doses. After Day 22, participants should return to their original dose schedule.

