- f Response assessment at EOT visit not required if performed within the last 30 days or progressive disease has been documented. After disease progression (including treatment failure by IWG criteria and relapse after CR or PR), response assessment will focus on evaluation of transformation to AML.
- g Paper PROs will be administered in this study: The FACT-Anemia questionnaire, the EQ-5D-5L, the PGIS, and the PGIC will be administered. The participant should complete these questionnaires before other study procedures at required visits. FACT-Anemia and EQ-5D-5L should be implemented prior to PGIS/PGIC. FACT-Anemia, EQ-5D-5L, the PGIS, and the PGIC should also be collected during long-term follow-up prior to initiation disease progression or initiation of a new anticancer therapy.
- h Report all AEs through the Safety Follow-up Visit/Call and any treatment-related SAEs thereafter.
- i Collect blood transfusions until start of new anticancer therapy.
- j Collect new anticancer therapy data following the last dose of study treatment.
- k For participants who do not initiate new anticancer therapy after the last dose. See Section [5.1.10](#) for adverse event reporting details.

Table 6. Schedule of Assessments - Repriming (Required After > 4 Weeks Have Lapsed Since the Last Dose of Magrolimab/Placebo Delays)

Visit Window (Days)	Day										
	1	2	3	4	5	6	7	8	11	15	22
	-	-	± 3	± 3	± 3	± 3	± 3	± 3	± 3	± 3	± 3
Pregnancy test	X										
CBC with differential, platelets, and reticulocytes ^{a,b}	X	X		X				X	X	X	X
Haptoglobin and LDH	X							X			
Serum or plasma chemistry ^a	X							X		X	X
Peripheral smear ^{a,c}	X	X							X		
Peripheral blood for biomarker studies ^d	X							X			
PK ^d	X							X			
Antidrug antibodies ^a	X										
Vital signs ^c	X	X						X		X	X
Symptom-directed physical examination ^a	X							X		X	
Adverse events	X	X	X	X	X	X	X	X	X	X	X
Concomitant medications	X	X	X	X	X	X	X	X	X	X	X
Blood transfusions	X	X	X	X	X	X	X	X	X	X	X
Premedication ^f	X			X				X	X		
Magrolimab/placebo: repriming ^g	X			X				X	X	X	X

Abbreviations: CBC = complete blood count; ECOG = Eastern Cooperative Oncology Group; LDH = lactate dehydrogenase; PK = pharmacokinetic(s); PRO = patient-reported outcome; WBC = white blood cell.

a Pretreatment assessments are to be collected within 24 hours prior to study treatment administration.

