Participants may continue study treatment until they show evidence of disease progression (including treatment failure by IWG criteria or relapse after PR/CR), loss of clinical benefit, or unacceptable toxicity (further details about treatment discontinuation in Section 5.7.1).

Repriming for Magrolimab

Given the large CD47 antigen sink on normal cells, participants who have a long dose delay of magrolimab are required to be reprimed with magrolimab dosing to resaturate the CD47 antigen sink.

Repriming differs depending on where the participant is in their treatment period as follows:

- 1) For participants who have not reached Day 57 of magrolimab/placebo, a 2-week dose delay is permitted.
- 2) For participants who have received Day 57 (or beyond) of magrolimab/placebo, a 4-week dose delay is permitted.

The repriming cycles are stand-alone cycles. After Day 22 of the repriming cycle, participants should return to their original dose schedule. Table 6 illustrates the repriming magrolimab dosing regimen and schedule of assessments.

Modifications to the study treatment doses administered should be made for a > 10% change in body weight from baseline and according to local and regional prescribing standards. Dose modifications for changes in body weight $\leq 10\%$ may be made according to local institutional guidelines. In the event that a dose is modified due to a > 10% weight change, the weight on which the new dose is based, will become the new baseline weight.

Please notify the blinded Medical Monitor of any planned dose delays. If either magrolimab or azacitidine is dose delayed for > 8 weeks for any reason, the Investigator must consult with the Sponsor's Medical Monitor prior to reinitiating study treatment.

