6.7.1.2. Treatment Delays

A treatment delay is defined as a non-protocol-specified interruption from treatment.

Treatment with magrolimab/placebo may be withheld if a \geq Grade 3 magrolimab/placebo-related AE occurs that does not resolve to \leq Grade 2 or baseline value within 14 days of onset. Magrolimab/placebo dosing may also be delayed for participants who experience hospitalization due to an AE that may preclude safe administration of magrolimab/placebo (e.g., intensive care unit admissions, significant bleeding events, severe infections, or other such events). In general, magrolimab/placebo should be continued/restarted without dose reduction. A dose delay for up to 3 days during the first 28 days may be permissible if the participant's WBC count is $> 20 \times 10^3/\mu\text{L}$ (applicable to each dose in the first 28 days: Day 1, Day 4, Day 8, Day 11, Day 15, and Day 22), to allow for oral hydroxyurea or etoposide treatment to reduce the WBC count. Magrolimab/placebo dosing may be delayed for AEs; however, starting at maintenance dose, dose delays of up to 4 weeks for other reasons may be allowed at the discretion of the Investigator and Sponsor. Participants with a treatment delay of longer than 4 weeks must undergo intraparticipant dose escalation (repriming; see Table 6 and Section 6.4) again.

Ongoing data analysis across magrolimab + azacitidine trials show that Q2W dosing of magrolimab without significant dose delays is important to yield optimal efficacy. In the event that dose delay is considered due to azacitidine related-toxicities (e.g., cytopenias) or other scenarios, magrolimab/placebo dosing should proceed as per Schedule of Assessment for treatment period - Magrolimab dosing (Table 4). Magrolimab/placebo dose may be delayed in case of serious adverse events or adverse events clearly related to magrolimab/placebo; in the event of magrolimab/placebo delay, dosing should resume as soon as it is clinically appropriate and logistically possible, without waiting to align with the participants' original Q2W schedule.

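### The Table 6 title gives a single repriming trigger of more than 4 weeks and, however it is read, omits the 2-week delay limit that Section 6.4 sets before Day 57

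*Protocol*

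**What the plan says.** Three places in the protocol state when repriming is needed.

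- **Section 4.3, Table 6 title.** Repriming is "Required After > 4 Weeks Have Lapsed Since the Last Dose of Magrolimab/Placebo Delays". The same wording appears in the protocol's list of tables and as the title of SAP Appendix Table 5, so it is not a fault of text extraction.
- **Section 6.4, Repriming for Magrolimab.** The rule is that "participants who have a long dose delay of magrolimab are required to be reprimed with magrolimab dosing". It continues: "Repriming differs depending on where the participant is in their treatment period as follows". The two limits follow: "For participants who have not reached Day 57 of magrolimab/placebo, a 2-week dose delay is permitted"; and "For participants who have received Day 57 (or beyond) of magrolimab/placebo, a 4-week dose delay is permitted". The section adds that "Table 6 illustrates the repriming magrolimab dosing regimen and schedule of assessments".
- **Section 6.7.1.2, Treatment Delays.** The definition is: "A treatment delay is defined as a non-protocol-specified interruption from treatment". For maintenance, "starting at maintenance dose, dose delays of up to 4 weeks for other reasons may be allowed at the discretion of the Investigator and Sponsor". The next sentence makes repriming mandatory when a delay exceeds 4 weeks. It does not restrict that to maintenance, but it refers the reader to both Table 6 and Section 6.4.

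**The concern.** The title runs a count from the last dose together with a count of delay, so it does not define a usable clock. It also carries one threshold where 6.4 has two. Table 6 is the schedule a site would open when a participant returns after a gap, and its title says that repriming is required under a stated condition.

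The trigger decides who receives re-escalation, mandatory premedication (Section 6.5) and 1-hour post-infusion monitoring (Section 6.4). Section 6.4 gives the reason for repriming as resaturating the CD47 antigen sink, and Section 7.10.1.1 reports hemoglobin falls of 2 to 3 g/dL or more at early doses. A participant before Day 57 who is judged by the title alone could restart without steps that 6.4 requires.

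**Working it through.** No sample size, power or alpha figure is involved. The check is day arithmetic, ignoring the ±3-day visit window.

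**Inputs**
- Dosing intervals (Section 6.4): doses on Days 1, 4, 8, 11 and 15 are 3, 4, 3 and 4 days apart; 7 days from Day 15 to Day 57; 14 days from Day 57.
- Section 6.4 limits: delay over 14 days before Day 57; delay over 28 days from Day 57. Section 6.4 says that a long delay requires repriming and then lists these as the permitted delays, so exceeding them is taken as the trigger.
- Title: either more than 28 days since the last dose, or a delay of more than 28 days.

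**Formula.** If delay counts from the missed scheduled dose, days since last dose = interval + delay. If delay counts from the last dose, the two are equal.

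| Title counts | Delay counts from | Before Day 57, weekly dosing: delays over the 6.4 limit that the title misses | Maintenance |
|---|---|---|---|
| from last dose | scheduled dose | title triggers at delay > 28 − 7 = 21, so 15-21 days are missed | title triggers at delay > 28 − 14 = 14; 6.4 and 6.7.1.2 at > 28; disagree for delays of 15-28 days (29-42 days since last dose) |
| delay | scheduled dose | title triggers at delay > 28, so 15-28 days are missed | agree |
| from last dose, or delay | last dose | title triggers at > 28 days, 6.4 at > 14, so 15-28 days are missed | agree |

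On the shorter early intervals, the first row becomes 28 − 4 = 24 (15-24 days missed) and 28 − 3 = 25 (15-25 days missed). The 6.7.1.2 sentence taken alone has the same gap as the second or third row: 15-28 days.

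**Example that does not depend on the reading.** Last dose Day 22, next due Day 29, return on Day 47. Delay from the scheduled dose is 47 − 29 = 18 days; time since last dose is 47 − 22 = 25 days.
- Section 6.4: 18 > 14 and 25 > 14, so reprime on either count.
- Title: 18 ≤ 28 and 25 ≤ 28, so no repriming on either count.

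Over the next 22 days, repriming means infusions on Days 1, 4, 8, 11, 15 and 22 of the Table 6 schedule: 6 infusions, the first 4 premedicated. Weekly resumption means Days 1, 8, 15 and 22: 4 infusions. None of those 4 carries mandated premedication, because the first 4 doses are past (assuming no earlier Grade 3 infusion reaction), and none carries mandated post-infusion monitoring, because the first 28 days are past.

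**The case against.** The strongest answer is that Section 6.4 governs. It is the dosing section, it states both limits, and it gives Table 6 only an illustrative role. In 6.7.1.2 the repriming sentence directly follows one confined to maintenance and points back to 6.4. Planned delays must be notified to the blinded Medical Monitor. A mistake therefore needs a site to act on a table title, or on one sentence, without following the cross-reference. Most of this stands, and it is why the point is minor. What remains is that none of the three texts states an order of precedence, 6.7.1.2 cites Table 6 and 6.4 together although they differ, and notifying the Medical Monitor does not say which threshold applies.

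A reader might go further and infer that the title contradicts the 4-week maintenance delay in 6.4 and 6.7.1.2. The documents do not support that as a firm finding. It needs the title to count from the last dose, setting aside its final word, and delay to count from the missed scheduled dose. The definition in 6.7.1.2 leans toward the second condition but names no starting day. If the title means delay, or if delay also counts from the last dose, the texts agree in maintenance.

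A reader might also treat counting from the scheduled dose as settled and write it into the title. That would fix up to 14 + 28 = 42 days without drug in maintenance before repriming. No section states that starting point, and the CD47 rationale could equally favor time since last dose. It is a clinical decision, not a text correction.

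**Conclusion.** The point holds for the period before Day 57 and does not depend on how the title is parsed: in every row of the table, some delays that require repriming under 6.4 fall short of the title's trigger. In maintenance there is an ambiguity, which becomes a conflict under only one combination of counting rules.

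The size is a range of days. The documents do not say how often such delays occur, so no number of affected participants can be given. The day ranges ignore visit windows and rest on reading the delays permitted in 6.4 as its repriming limits, which is how that section is laid out. This is a minor dosing-safety inconsistency that is worth correcting. It has no bearing on the primary endpoints, the alpha allocation or power.

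**What to change.** 1. Retitle Table 6: *Required after a magrolimab/placebo dose delay of > 2 weeks before Day 57 or > 4 weeks from Day 57 onward*.
2. Put the same two limits in the repriming sentence of 6.7.1.2.
3. Have the clinical team state once, in 6.4, whether a delay is counted from the last dose or from the missed scheduled dose.
4. Match the title of SAP Appendix Table 5 at the next SAP revision, for consistency only.

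Items 1 and 2 change one title and one sentence to limits that 6.4 already sets. Item 3 needs a short clinical decision and one added sentence. A brief clarification to sites would carry all three. No design or analysis change follows.

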4.4. Design Rationale

This study is a randomized, double-blind, placebo-controlled, multicenter study designed to evaluate the efficacy and safety of magrolimab + azacitidine compared with that of azacitidine + placebo in previously untreated participants with intermediate/high/very high risk MDS by IPSS-R. The primary efficacy endpoints of this study are CR rate and OS. This trial is designed to adequately determine the efficacy of magrolimab + azacitidine compared with azacitidine + placebo based on CR rate and OS, which are both standard approvable endpoints for this participant population. The CR rate of azacitidine monotherapy is well benchmarked in several prospective studies in higher risk MDS. Based on large historical studies, the CR rate of azacitidine monotherapy ranges from 6% to 17%, accounting for analysis under the IWG criteria (azacitidine US package insert, {Fenaux 2009, Silverman 2006}). One additional study evaluating azacitidine demonstrated a CR rate of 24%; however, this study also included lower risk MDS by IPSS-R and chronic myelomonocytic leukemia participants; the CR rate specifically in higher risk MDS participants was not reported {Sekeres 2017}. Given the range of CR rates and median OS data for azacitidine reported in large historical studies, with approximately 520 participants randomized in a 1:1 ratio, this study is adequately powered to show a superior CR rate or OS for the experimental arm compared with the control arm, assuming a CR rate of 20% in the control arm and a CR rate of 39% in the experimental arm, and an OS of 18 months in the control arm and 25.4 months in the experimental arm. Randomization will be stratified by 3 factors: 1) geographic region (US versus ex-US sites), 2) cytogenetic risk status, and 3) bone marrow blast percentage. The second and third stratification factors are reported as determinants of response and duration for azacitidine monotherapy based on a large retrospective analysis in higher risk MDS {Itzykson 2011}.

4.5. Recruitment

Approximately 200 sites in the US, Australia, Europe, and other countries as required, based on enrollment and study timelines, will be included in this study. A total of approximately 520 participants will be enrolled for the 2 primary analyses of CR rate and OS.

All participants must be provided an informed consent form (ICF) describing the study with sufficient information for participants to make an informed decision regarding their participation. Participants must sign the institutional review board (IRB)/independent ethics committee (IEC) approved ICF prior to participation in any study-specific procedure. Data from assessments performed as part of SOC prior to ICF signature may be used if they are within the required Screening period. The participant must receive a copy of the signed and dated consent documents. A signed copy of the consent documents must be retained in the site file.

Once participants sign the ICF, they enter the Screening Period for the study and receive a unique patient identification number before any study procedures are performed. This number is used to identify the participant throughout the clinical study and must be used on all study documentation related to that participant, including if a participant is rescreened.

Participant screening laboratory assessments may be repeated beyond the initial screening assessments within the 30-day Screening Period. Participants who fail screening may undergo repeated screening if the participant's medical condition has changed. However, once a participant has been randomized, that participant cannot be rerandomized.

All participants who provide informed consent must be registered in the electronic data capture (EDC) and interactive voice/web/mobile response system (IXRS) systems, including any screen failures.

4.6. Definitions of Enrollment and Screen Failure

Participants officially enter the Screening Period following provision of informed consent. After signing the ICF, eligible participants must be randomized within 30 days. Treatment will start within 72 hours after randomization.

A participant is defined as enrolled in the study when that participant has been randomized.

A screen failure is a consented participant who has been deemed ineligible on the basis of 1 or more eligibility criteria or who has withdrawn consent prior to randomization. Screen failures may be rescreened if the participant's medical condition has changed.

4.7. Inclusion Criteria

To be included in this study, each individual must satisfy all the following criteria:

- 1) Participants with MDS defined according to World Health Organization classification, with an IPSS-R {[Greenberg 2012](#)} prognostic risk category of intermediate, high, or very high risk. Note: participants who require AML-like therapy are not eligible.
- 2) White blood cell (WBC) count $\leq 20 \times 10^3/\mu\text{L}$ prior to randomization. If the participant's WBC is $> 20 \times 10^3/\mu\text{L}$ prior to randomization, the participant can be randomized, assuming all other eligibility criteria are met. Of note, while this does not impact eligibility, please ensure that the WBC is $\leq 20 \times 10^3/\mu\text{L}$ prior to the first dose of study treatment and prior to each magrolimab/placebo dose for priming doses of magrolimab.
 - a) Participants can be treated with hydroxyurea (up to 4 g/day) throughout the study or prior to randomization to reduce the WBC to $\leq 20 \times 10^3/\mu\text{L}$ to enable eligibility and magrolimab dosing. Oral etoposide (up to 200 mg orally per day) may be given as an alternative to hydroxyurea for participants who are intolerant to hydroxyurea or cannot achieve sufficient WBC lowering on hydroxyurea.
- 3) Participant has provided informed consent.
- 4) Participant is willing and able to comply with clinic visits and procedures outlined in the study protocol.
- 5) Male or female, age ≥ 18 years.
- 6) Eastern Cooperative Oncology Group (ECOG) performance score of 0 to 2.

- 7) Willing to undergo blood transfusions as deemed clinically necessary.
- 8) Pretreatment blood cross-match including ABO (any of the 4 blood groups A, B, AB, and O comprising the ABO system)/Rh (Rhesus factor), DAT (direct antiglobulin test), and phenotyping or genotyping completed (as detailed in Section 5.1.4).
- 9) Biochemical indices within the ranges shown below:
 - b) Aspartate aminotransferase (AST)/serum glutamic oxaloacetic transaminase and alanine aminotransferase (ALT)/serum glutamic pyruvic transaminase $\leq 3.0 \times$ upper limit of normal (ULN)
 - c) Total bilirubin $\leq 1.5 \times$ ULN or $3.0 \times$ ULN and primarily unconjugated if participant has a documented history of Gilbert's syndrome or genetic equivalent
 - d) Serum creatinine $\leq 1.5 \times$ ULN or calculated glomerular filtration rate (GFR) ≥ 40 mL/min/1.73 m²
- 10) All participants must have a documented hemoglobin ≥ 9 g/dL within 24 hours prior to the first 2 doses of magrolimab/placebo infusion. Participants who do not meet these criteria must be transfused and have their hemoglobin rechecked to meet the minimum hemoglobin threshold prior to administering each of the first 2 doses of magrolimab/placebo. Transfusions are allowed in order to meet hemoglobin eligibility (see Section 7.10.1.1).
- 11) Female participants of childbearing potential must not be nursing or planning to be pregnant and must have a negative urine or serum pregnancy test within 30 days before randomization and within 72 hours before the first administration of study treatment.
- 12) Male participants and female participants of childbearing potential who engage in heterosexual intercourse must agree to use protocol-specified method(s) of contraception as described in Appendix G.
- 13) Willing to consent to mandatory pretreatment and on-treatment bone marrow biopsies (trephines), unless not feasible as determined by the Investigator and discussed with the Sponsor.

4.8. Exclusion Criteria

If an individual meets any of the following criteria, he or she is ineligible for this study:

- 1) Prior treatment with CD47 or SIRP α -targeting agents.
- 2) Prior therapy for the treatment of MDS with an IPSS-R prognostic risk category of intermediate, high or very high risk (excluding hydroxyurea or oral etoposide), prior treatment with hypomethylating agents and/or low dose cytarabine. NOTE: Localized noncentral nervous system (CNS) radiotherapy, erythroid and/or myeloid growth factors, previous hormonal therapy with luteinizing hormone-releasing hormone (LHRH) agonists for prostate cancer, and treatment with bisphosphonates and receptor activator of nuclear factor kappa-B ligand (RANKL) inhibitors are not criteria for exclusion. Prior lenalidomide is also not exclusionary.

- 3) Immediately eligible for an allogeneic SCT, as determined by the Investigator, with an available donor.
- 4) Contraindications to azacitidine, including advanced malignant hepatic tumors or known hypersensitivity to azacitidine or mannitol.
- 5) Known inherited or acquired bleeding disorders.
- 6) Previous SCT within 6 months prior to randomization, active graft-versus-host disease, or requiring transplant-related immunosuppression.
- 7) Clinical suspicion of active CNS involvement by MDS.
- 8) Significant medical diseases or conditions, as assessed by the Investigators and Sponsor, that would substantially increase the risk benefit ratio of participating in the study. This includes, but is not limited to, acute myocardial infarction within the last 6 months, unstable angina, uncontrolled diabetes mellitus, significant active infections, and congestive heart failure New York Heart Association Class III-IV.
- 9) Second malignancy, except treated basal cell or localized squamous skin carcinomas, localized prostate cancer, or other malignancies for which participants are not on active anticancer therapies and have had no evidence of active malignancy for at least ≥ 1 year.
- 10) History of psychiatric illness or substance abuse likely to interfere with the ability to comply with protocol requirements or give informed consent.
- 11) Pregnancy or active breastfeeding.
- 12) Known active or chronic hepatitis B or C infection or HIV infection in medical history.
- 13) Active hepatitis B virus (HBV) and/or active hepatitis C virus (HCV), and/or HIV following testing at Screening:
 - a) Participants who test positive for hepatitis B surface antigen (HBsAg). Participants who test positive for hepatitis B core antibody (anti-HBc) will require HBV DNA by quantitative polymerase chain reaction (PCR) for confirmation of active disease.
 - b) Participants who test positive for HCV antibody. These participants will require HCV RNA by quantitative PCR for confirmation of active disease.
 - c) Participants who test positive for HIV antibody.
 - d) Participants not currently on antiviral therapy and who have an undetectable viral load in the prior 3 months may be eligible for the study.

